APPENDIX E PATIENT'S MEDICATION DIARY

| |
|--------------------------------|
| CTEP-assigned Protocol # _____ |
| Local Protocol # _____ |

Today's date _____

Agent: MK-2206

Patient Name _____ (initials acceptable)

Patient Study ID _____

INSTRUCTIONS TO THE PATIENT:

1. Complete one form for each cycle of treatment.
2. You will take MK-2206 tablets via mouth once weekly. You should take the tablets 2 hours before or after a meal
 Dose: take ___ mg tablets, ___ mg tablets, and ___ mg tablets.
3. Record the date, the number of tablets of each size of tablet that you took, and when you took them.
4. If you have any comments or notice any side effects, please record them in the Comments column.
5. Please bring this form and your bottles of MK-2206 tablets when you return for each appointment.

| Day | Date | Time of dose | # of tablets taken | | | Comments |
|-----|------|--------------|--------------------|----|----|----------|
| | | | mg | mg | mg | |
| 1 | | | | | | |
| 2 | | | | | | |
| 3 | | | | | | |
| 4 | | | | | | |
| 5 | | | | | | |
| 6 | | | | | | |
| 7 | | | | | | |
| 8 | | | | | | |
| 9 | | | | | | |
| 10 | | | | | | |
| 11 | | | | | | |
| 12 | | | | | | |
| 13 | | | | | | |
| 14 | | | | | | |
| 15 | | | | | | |
| 16 | | | | | | |
| 17 | | | | | | |
| 18 | | | | | | |
| 19 | | | | | | |
| 20 | | | | | | |
| 21 | | | | | | |
| 22 | | | | | | |
| 23 | | | | | | |
| 24 | | | | | | |
| 25 | | | | | | |
| 26 | | | | | | |
| 27 | | | | | | |
| 28 | | | | | | |

Patient's signature _____

Physician's Office will complete this section:

1. Date patient started protocol treatment
2. Date patient was removed from study
3. Patient's planned total daily dose
4. Total number of tablets taken this month
5. Physician/Nurse/Data Manager's Signature

APPENDIX F PATIENT'S MEDICATION DIARY

| |
|--------------------------------|
| CTEP-assigned Protocol # _____ |
| Local Protocol # _____ |

Today's date _____ Agent: Everolimus
 Patient Name _____ (initials acceptable) Patient Study ID _____

| INSTRUCTIONS TO THE PATIENT: | | | | |
|--|------|--------------|--------------------|----------|
| 1. Complete one form for each cycle of treatment. | | | | |
| 2. You will take Everolimus 10 mg every day at the same time with or without food. Dose: take 2 (5 mg tablets) or 1 (10mg tablet) | | | | |
| 3. Record the date, the number of tablets of each size of tablet that you took, and when you took them. | | | | |
| 4. If you have any comments or notice any side effects, please record them in the Comments column. | | | | |
| 5. Please bring this form and your bottles of MK-2206 tablets when you return for each appointment. | | | | |
| Day | Date | Time of dose | # of tablets taken | Comments |
| | | | 5 or 10 mg | |
| 1 | | | | |
| 2 | | | | |
| 3 | | | | |
| 4 | | | | |
| 5 | | | | |
| 6 | | | | |
| 7 | | | | |
| 8 | | | | |
| 9 | | | | |
| 10 | | | | |
| 11 | | | | |
| 12 | | | | |
| 13 | | | | |
| 14 | | | | |
| 15 | | | | |
| 16 | | | | |
| 17 | | | | |
| 18 | | | | |
| 19 | | | | |
| 20 | | | | |
| 21 | | | | |
| 22 | | | | |
| 23 | | | | |
| 24 | | | | |
| 25 | | | | |
| 26 | | | | |
| 27 | | | | |
| 28 | | | | |

Patient's signature _____

| |
|--|
| Physician's Office will complete this section: 1. Date patient started protocol treatment 2. Date patient was removed from study 3. Patient's planned total daily dose |
|--|

NCI Protocol #: 8727
Version Date: June 11, 2018

- | |
|---|
| 
4. Total number of tablets taken this month5. Physician/Nurse/Data Manager's Signature |
|---|

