5.1.2 Everolimus (Arm B)

Everolimus is an oral drug that will be administered once daily. Patients should take everolimus at a starting dose of 10 mg orally once daily. Patients will be instructed to take everolimus in the morning, at the same time each day.

A study cycle will be 4 weeks in length.

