6.1 MK-2206

| Dose Level | MK2206 Dose |
|-------------------|------------------|
| -2 | 90 mg PO weekly |
| -1 | 135 mg PO weekly |
| 0 (starting dose) | 200 mg PO weekly |

Clinically significant Grade 3 side effects attributable to MK2206 will require dose withholding until grade 1 levels of toxicity are reached. At that point drug can be restarted at the next lower dose level. If after four weeks the toxicity remains completely controlled, dose re-escalation can be attempted at the treating physician's discretion.

If toxicity does not resolve to a grade 1 or lower levels within four weeks of drug discontinuation, the patient will be taken off study.

Clinically significant Grade 4 side effects attributable to MK2206 which are considered medically relevant will result in patient being taken off study.

Management of Hyperglycemia

Grade 3 hyperglycemic events (>250 mg/dL) should lead to consultation with an endocrinologist or other specialist. If glucose levels do not return to grade 1 or lower within one week of appropriate therapy, patients should be considered to have a DLT.

Appropriate therapy will usually involve oral antihyperglycemic agents, since the inhibition of glucose transport into the cell by AKT/mTOR inhibitors may render insulin ineffective. The goal of therapy is to keep fasting glucose <150 mg/dL, random blood glucose levels <180 mg/dL, and Hemoglobin A1c <8%. Glucose monitoring should be performed weekly, during the first cycle of therapy, and on day 1 of subsequent cycles, prior to drug administration.

Hemoglobin A1c monitoring, for patients requiring treatment of hyperglycemia, should be

performed with each cycle of MK-2206 therapy.

Management of Rash

Patients who develop grade 3 rash will have treatment withheld as outlined above. For patients with persistent grade 2 rash that does not respond to conservative measures, and which in the opinion of the treating physician is significantly compromising quality of life, dose can be held, and once rash reaches grade 1 intensity or lower, MK2206 can be restarted at the same dose level. If a second dose withholding is required for redevelopment of persistent refractory grade 2 rash, dose can be withheld and then restarted at one dose level lower once rash reaches a grade 1 or lower level. MK2206 re-escalation can be attempted after 4 weeks if in the judgment of the treating physician the patient's side effect profile warrants re-escalation.

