6.2 Everolimus

Table 3 Everolimus dose level modification guidelines

| Dose level | Dose and schedule |
|-------------------|---------------------|
| 0 (starting dose) | 10 mg daily |
| -1 | 5 mg daily |
| -2 | 5mg every other day |

Table 4 Criteria for dose-modification in case of suspected toxicity and reinitiation of everolimus treatment

| Toxicity | Actions |
|---|--|
| 
Non-hematological toxicity
 
Grade 2 (pneumonitis – refer to Table 5)
 
Grade 3 (hyperlipidemia*) (pneumonitis – refer to Table 5)
 
Grade 4
 | 
If the toxicity is tolerable to the patient, maintain the same dose. If the toxicity is intolerable to patient, interrupt everolimus until recovery to grade ≤ 1.
 
Then reintroduce everolimus at same dose. If event returns to grade 2, then interrupt everolimus until recovery to grade ≤ 1. Then reintroduce everolimus at the lower dose level.
 
Interrupt study drug until recovery to grade ≤ 1. Then reintroduce everolimus at the lower dose level. For pneumonitis consider the use of a short course of corticosteroids.
 
Discontinue everolimus.
 |
| 
Hematological toxicity
 
Grade 2 Thrombocytopenia (platelets $<75, \geq 50 \times 10^9/L$)
 | 
Interrupt study drug until recovery to grade ≤ 1 ($>75 \times 10^9/L$). Then reintroduce study drug at initial dose. If thrombocytopenia again returns to grade 2, interrupt study drug until recovery to grade ≤ 1. Then reintroduce study drug at the lower dose level.
 |

| | |
|---|--|
| Grade 3 Thrombocytopenia (platelets $<50, \geq 25 \times 10^9/L$) | Interrupt study drug until recovery to grade ≤ 1 (platelets $\geq 75 \times 10^9/L$). Then resume study drug at one dose level lower. If grade 3 thrombocytopenia recurs, discontinue study drug. |
| Grade 4 Thrombocytopenia (platelets $< 25 \times 10^9/L$) | Discontinue study drug. |
| Grade 3 Neutropenia (neutrophils $<1, \geq 0.5 \times 10^9/L$) | Interrupt study drug until recovery to grade ≤ 1 (neutrophils $\geq 1.5 \times 10^9/L$). Then resume study drug at the initial dose. If ANC again returns to Grade 3, hold study drug until the ANC $\geq 1.5 \times 10^9/L$. Then resume study drug dosing at the lower dose level. Discontinue patient from study therapy for a third episode of grade 3 neutropenia. |

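### The everolimus diary prints 10 mg every day for every cycle, which is wrong for any patient whose dose has been reduced

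*Combined protocol and SAP*

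**What the plan says.** Appendix F is the diary for Arm B, with one form for each cycle. Item 2 of its patient instructions reads "You will take Everolimus 10 mg every day at the same time with or without food", followed by "Dose: take 2 (5 mg tablets) or 1 (10mg tablet"). Both tablet options come to 10 mg.

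The treatment sections are broader. Section 5.1.2 states: "Patients should take everolimus at a starting dose of 10 mg orally once daily". Table 3 in Section 6.2 lists level 0 (10 mg daily), level -1 (5 mg daily) and level -2 ("5mg every other day"). Table 4 directs, for example after grade 3 non-hematological toxicity and recovery: "Then reintroduce everolimus at the lower dose level". Table 5 allows a restart at a reduced dose after grade 2 or 3 pneumonitis.

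The MK-2206 diary in Appendix E is built differently. It prints the route and frequency ("You will take MK-2206 tablets via mouth once weekly") and leaves tablet strengths and numbers blank.

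**The concern.** The diary is the sheet the patient takes home, and its instruction does not change when the prescribed dose does. For a patient restarted at a lower level, the printed dose contradicts the prescription. At level -2 the printed frequency does too. The patients exposed are those whose dose was cut because of toxicity, and the form points them back to the dose that preceded it.

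What is at stake is patient safety and the accuracy of the dosing record; Appendix K lists signed and dated pill diaries among the source documents for audit.

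There is also a clerical slip. Item 5 of the everolimus diary says "Please bring this form and your bottles of MK-2206 tablets when you return for each appointment". Arm B patients receive no MK-2206, and Section 8.2 describes everolimus as supplied in blisters. This adds no dosing risk.

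**Working it through.** The plan gives no figure to reproduce. The check compares the form with the dose tables and then works out the dose per cycle.

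**Inputs**
- Printed dose: 10 mg every day (Appendix F, item 2).
- Dose levels: 10 mg daily, 5 mg daily, 5 mg every other day (Table 3).
- Cycle length: 4 weeks, or 28 days (Section 5.1.2).
- Planned everolimus arm: 35 patients (Section 13.2).
- Tablets: 5 mg and 10 mg, 28 per pack (Section 8.2).

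**Does the printed line fit each level?**

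| Diary | Level 0 | Level -1 | Level -2 | Fits |
|---|---|---|---|---|
| Everolimus (prints 10 mg every day) | yes | no: dose | no: dose and frequency | 1 of 3 |
| MK-2206 (dose blank, prints weekly) | yes | yes | yes | 3 of 3 |

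The MK-2206 form fits throughout because all its levels are weekly (200, 135 and 90 mg), down to "90 mg PO weekly" at level -2.

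**Dose over one 28-day cycle** = mg per dose × number of doses
- Printed line: 10 × 28 = 280 mg.
- Level -1: 5 × 28 = 140 mg. Ratio 280/140 = 2; excess 280 − 140 = 140 mg.
- Level -2: 5 × 14 = 70 mg. Ratio 280/70 = 4; excess 280 − 70 = 210 mg.

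**Sensitivity to tablet supply.** The documents do not say what is dispensed to a reduced patient. Assume, for illustration, a single pack of 28 tablets of 5 mg and no leftover tablets: 28 × 5 = 140 mg is available.
- Level -1: two tablets a day exhausts the pack in 28/2 = 14 days. The cycle total is 140 mg, so there is no excess over the cycle, but the daily dose is doubled for those 14 days.
- Level -2: at most 140/70 = 2 times the intended cycle total.

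Leftover 10 mg tablets or a larger supply would allow more, up to the full 2 and 4 times. Under these assumptions the cycle-total ratio ranges from 1 to 2 at level -1 and from 2 to 4 at level -2, for a patient who follows the printed line for as long as tablets last.

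**The case against.** The strongest reply is that the diary records doses and does not set them. Section 5.1 describes it as a log, Sections 5.1.2 and 6.2 govern the dose, and a reduction follows an interruption and a restart directed by the clinician. The form can also record reduced dosing. Its tablet column is headed for 5 or 10 mg, it has a row for each day, and the office section has a line for the planned total daily dose. Sites enter the dose for each course, and audit checks dose modifications against the protocol. Dispensing labels and site instructions are not in the documents, so a reduced patient may receive correct written directions elsewhere. The blanks in the MK-2206 form may reflect its several tablet strengths rather than any provision for reductions.

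Much of this stands. It makes an overdose less likely, and the supply point makes 2 and 4 times upper limits. It does not correct the instruction. A form with 5 mg in the planned-dose line would still tell the patient to take 10 mg, and a total daily dose describes alternate-day dosing poorly. Being able to record a reduced dose differs from being told to take it. Dose entry and audit come after the event. Visits are every 4 weeks, or may be every 12 weeks for patients progression-free after 1 year. Whatever the reason for the Appendix E blanks, they show that the format is workable.

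**Conclusion.** The concern holds. The instruction is right at the starting dose and wrong at both reduced levels, in dose at level -1 and in dose and frequency at level -2. Under the printed line, a full cycle with unrestricted supply would give 2 times the intended total at level -1 and 4 times at level -2.

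This is a conditional risk for individual patients, limited to those reduced among the 35 planned for the arm. The documents give neither the expected number of reductions nor the chance that a patient would follow the form over the clinic's advice, so no expected number of overdoses can be stated. Nothing here bears on PFS, power, error rates, stopping rules or the primary analysis. The form should be corrected; the item 5 slip is clerical and carries no weight in that judgment.

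**What to change.** In Appendix F item 2, replace the fixed dose and tablet count with blanks for:
- dose in mg;
- tablet strength and number of tablets;
- frequency, daily or every other day. This needs its own blank because level -2 changes the schedule.

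State that the site completes these at the start of each cycle, and again at any change within a cycle, from the patient's current Table 3 level. In item 5, ask for everolimus tablets in their blister packs instead of MK-2206 bottles.

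The cost is one revised page, largely modelled on Appendix E. No dose level and no analysis changes.

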APPENDIX G SNP ANALYSIS

1. Collection of Specimen(s)

If patient consents to optional procedure(s), at least 2 and as many as 5 formalin fixed paraffin embedded blocks from nephrectomy will be acquired from each patient participating in the study. These blocks will be used for TMA analysis and for virtual karyotyping. A detailed laboratory manual will be provided.

2. Handling of Specimens(s)

Specimens need to be kept at ambient temperatures, and reasonable efforts should be undertaken to avoid exposure to temperature extremes. If necessary, samples may be shipped on gel packs to avoid extreme temperatures.

3. Shipping of Specimen(s)

Samples will be batch shipped to the University of Texas M. D. Anderson Cancer Center. All samples will be transported according to applicable IATA regulations.

Samples will be shipped to:

[name]
University of Texas M. D. Anderson Cancer Center
[name]
[name]
[contact]
[contact]
[contact]

Once received, samples will be distributed to UTMDACC core facility for analysis.

4. Site(s) Performing Correlative Study

The analysis will be performed at UTMDACC core facility.

- 5. Methods in brief:** An area with at least 80% tumor content will be marked on the H&E slide from paraffin embedded patient tissue, and this area will be manually microdissected from unstained slides. DNA extractions from the microdissected tissue will be performed with the Qiagen DNA Easy Kit (Qiagen, Valencia, CA) with modifications for FFPE tissue. DNA will be analyzed for chromosome copy number (CCN) changes and loss of heterozygosity (LOH) with the Affymetrix 250K Nsp SNP Genotyping arrays (Affy250KNsp) following a modified protocol.

Data acquired from the Affymetrix GeneChip Operating System v4.0 (GCOS) will be analyzed using Affymetrix's Genotyping Console v2.1. The quality control parameters for each sample will be signal detection rate (the percentage of features in the array that show adequate fluorescence intensity) and the SNP call rate (rate of successful allele identification). LOH and copy number estimates will be obtained using a publicly available analysis package: Copy Number Analyzer for Affymetrix GeneChip arrays (CNAG v3.3).

Chromosomal gains and losses will be determined by the copy number estimates assigned by the hidden Markov model (HMM) in CNAG. LOH will be determined based on the LOH likelihood score as determined with CNAG with a threshold likelihood of 12. Extent and boundaries of the chromosomal lesions will be recorded for each lesion in all tumor samples.

- 6. Statistical Analysis:** Univariate and multivariate Cox proportional hazards regression will be performed to model the effects of various chromosomal abnormalities, nuclear grade, pathologic stage, and clinical outcome (PFS, OS). Kaplan-Meier analysis and Cox regression will be performed using Stata 10 (College Station, TX).

Classification analysis will also be performed to identify profiles of chromosomal abnormalities that predict progression and death. Chromosomal abnormalities that are informative for classification will be identified by filtering with a Mahalanobis distance-based greedy plus-take-away-1 heuristic based on a sequential forward-backward stepwise procedure. Performance and area under the curve (AUC) will be compared by using k nearest neighbor, naive Bayes, linear/quadratic/Fisher's discriminant analysis, random forests, linear vector quantization, kernel regression, support vector machines, particle swarm optimization, and artificial neural networks. Random forests will be applied to pre-selected features, so the results will essentially represent the 0.632 bootstrap method.

For sample size determination, using PASS 2008 (Kaysville, UT) and a one-sided logrank test, for a sample size of N=60 (N=30 in the response group and N=30 in the non-response group), a median PFS of 3.5 months for non-response and 7.5 months for response, the hazard ratio is 2.14 and the power to reject the null hypothesis (one-sided alternative) that response PFS is equal to or more than median non-response PFS is 86.5%. Based on the patients proposed for this study and survival projections, we should be able to attain statistical power > 90%.

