Virtual Karyotyping as a Predictive Biomarker in RCC: RCC karyotypic changes have been associated with clinical outcome in primary RCC. Preliminary data suggest that a specific karyotypic profile is associated with response and resistance to antiangiogenic therapy (abstracts, manuscript in preparation). Evaluation of chromosomal regions to elucidate mechanisms behind the karyotypic observations is underway. The purpose of the current study is to confirm our observations in a cohort of patients previously treated with anti-VEGF therapy, and to determine whether karyotypic patterns are predictive for response or resistance in TORC1 or AKT blocking agents.

We hypothesize that (1) Patients who showed a short PFS on prior anti-VEGF therapy will have a distinct karyotype, (2) These patients will show benefit to AKT blocking agents, and (3) Further karyotypic discrimination will be possible between patients who benefit from AKT blockade versus mTOR blockade.

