13.4 Statistical Analysis Plan

The primary endpoint, progression-free survival (PFS), is defined as the time interval between date of treatment and date of disease progression, date of death or last follow-up date, whichever occurred first. The probability of PFS be estimated using the Kaplan-Meier method and will be compared between the two treatment arms using stratified log-rank test. Patients' safety data will be summarized by treatment arm, category, severity and relevance.

For secondary analyses, the Kaplan-Meier method will be used to estimate overall survival (OS) and time to failure (TTF), and stratified log-rank test will be used to compare between the two treatment arms. The OS is defined as the time interval between the date of treatment and the date of death or last follow-up, whichever occurred first. The TTF is defined as the time interval between the date of treatment and the date of disease progression, date of death, date of treatment discontinuation due to severe toxicity or last follow-up date, whichever occurred first. Overall response (OR) is defined as CR+PR and logistic regression model will be fit to assess the effect of treatment on the rate of OR.

Since the correlative studies being performed are by nature exploratory, and have not been

performed before in patients with RCC receiving mTOR inhibitors or AKT inhibitors, powering of these endpoints is not possible. Clinical benefit is defined as CR+PR+SD and again, we will fit logistic regression models to assess the effects of treatment, AKT activation, circulating cytokines and angiogenic factors, and karyotype on clinical benefit. The interaction effect between treatment and these exploratory factors will also be evaluated.

For virtual karyotyping, technique specific statistical analyses are outlined in [Appendix G](#).

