We are interested in changes in CAF levels from baseline (BL) that are associated with either tumor progression or are predictive of PFS. It is expected that approximately 80% of the patients will complete cycle 2. To identify potential markers of therapeutic resistance, we will fit linear mixed-effects models for each marker that is measured. These models will incorporate random effects that allow each individual patient to have his or her own natural level as well as a fixed binary effect for “progressed” versus “not progressed.” The significance of the fixed effect of progression is measured by an F-test. We will also explore more elaborate models that allow for a treatment effect that may distinguish changes on treatment from BL. To correlate changes in individual CAFs with clinical benefit from MK2206 vs. Everolimus, we will use Cox proportional hazards models. Primary analyses will use the differences in marker levels as continuous predictors. We will also explore the use of derived binary markers (“changed” or “unchanged”), where the thresholds for change will be set using mixed-effects linear models that incorporate repeated measures on the same individual patient. For the evaluation of markers to predict clinical benefit, we will take individual predictive markers and will combine them with the goal of identifying groups of patients with greater PFS and/or benefit. We will apply two different methods of analysis. First, we will fit multivariate Cox proportional hazards models that incorporate all individual markers that exhibit some predictive ability, using the Akaike Information Criterion (AIC) to eliminate markers that do not contribute significantly to the multivariate model. Second, we will apply robust clustering methods to identify subgroups of samples that exhibit similar CAF expression profiles, and test whether the resulting subgroups have different outcomes.

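### The PFS/OS Cox models for karyotype and cytokine markers specify no arm or arm-by-marker term, so they cannot separate prognostic from predictive markers

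*Combined protocol and SAP*

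**What the plan says.** **Models.** Appendix G item 6 plans univariate and multivariable Cox regression to "model the effects of various chromosomal abnormalities, nuclear grade, pathologic stage, and clinical outcome (PFS, OS"). Appendix I (Statistical Analysis) says "we will fit multivariate Cox proportional hazards models that incorporate all individual markers that exhibit some predictive ability", with AIC used to drop markers. No arm, arm-by-marker term or stratification factor is named in either place. For changes in cytokines and angiogenic factors (CAF), Appendix I says "To correlate changes in individual CAFs with clinical benefit from MK2206 vs. Everolimus, we will use Cox proportional hazards models". That states a comparison between drugs but writes out no arm or interaction term. The one explicit mention of treatment, "We will also explore more elaborate models that allow for a treatment effect that may distinguish changes on treatment from BL", belongs to the linear mixed models of marker levels, not to the Cox models.

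**Questions asked.** Section 2.5 wants to "determine whether karyotypic patterns are predictive for response or resistance in TORC1 or AKT blocking agents", and its third karyotype hypothesis concerns telling patients who benefit from AKT blockade from those who benefit from mTOR blockade. Appendix I gives as its primary goal predictive biomarkers of benefit, with benefit meaning longer PFS and OS. The objectives in Section 1.2 are milder: for karyotype, its impact on outcome; for CAF, prediction of clinical benefit.

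**Where the interaction is planned.** Section 13.4 fits logistic models for treatment, AKT activation, CAF and "karyotype on clinical benefit", defined as CR+PR+SD, and adds: "The interaction effect between treatment and these exploratory factors will also be evaluated". It then refers the reader onward: "For virtual karyotyping, technique specific statistical analyses are outlined in" Appendix G. MSKCC group and type of prior therapy are randomization strata (Section 13.3), and the stratified log-rank tests in Section 13.4 compare the arms.

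**The concern.** A marker is predictive when the effect of one drug relative to the other depends on it. On a time-to-event outcome, that is the arm-by-marker contrast. A marker effect estimated without arm is a mixture of the two arm-specific effects, weighted roughly 2:1 towards MK-2206. The same estimate can come from a marker that is prognostic under either drug or from one that matters under one drug only. Effects in opposite directions can cancel.

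At stake is the label put on a finding. A marker of generally poor prognosis could be reported as selecting patients for AKT blockade, and a marker with opposite effects could be missed. The primary comparison of the arms is not affected.

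**Working it through.** **1. Appendix G's own power figure.** Inputs from Appendix G: medians 3.5 and 7.5 months, 30 per group, one-sided log-rank test, stated power 86.5%. No alpha is given.
- HR = 7.5/3.5 = 2.143; log HR = 0.762.
- Freedman's formula at one-sided 0.05: power = Φ(√D × (HR − 1)/(HR + 1) − 1.645). With D = 57 events, 7.550 × 0.3636 − 1.645 = 1.100, giving 86.5%. With D = 60, 87.9%.
- For 48 to 60 events, one-sided 0.025 gives at most 83.9% and one-sided 0.10 at least 89.2%. The stated figure therefore implies one-sided 0.05, which is assumed below.

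**2. The figure above 90% for this trial.** Schoenfeld's formula for two marker groups, ignoring arm: power = Φ(0.762 × √(D p(1 − p)) − 1.645), where p is the share with the marker. With the trial's 75 events (Section 13.2) and p = 0.5, 0.762 × √18.75 − 1.645 = 1.655, giving 95%. At p = 0.3 it is 92%. Appendix G item 7 gives assay success of at least 76%; 0.76 × 75 = 57 events if every patient supplies tissue, and power is then 89% at p = 0.5. The figure is thus reachable, but for a two-group comparison that does not involve arm.

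**3. Power for the predictive question.** Variance of the log ratio of HRs = sum of 1/events over the four arm-by-marker cells. With events split 2:1 by arm this is 1/(D × 2/9 × p(1 − p)). Example: D = 75, p = 0.5 gives cells of 25, 25, 12.5 and 12.5; variance 0.04 + 0.04 + 0.08 + 0.08 = 0.24; SE 0.490; power Φ(0.762/0.490 − 1.645) = 46%. For a ratio of HRs of 2.14 at one-sided 0.05 (SE in brackets):

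| Events | p = 50% | p = 30% | p = 20% |
|---|---|---|---|
| 75 | 46% (0.490) | 41% (0.535) | 34% (0.612) |
| 57 | 39% (0.562) | 34% (0.613) | 29% (0.702) |

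At one-sided 0.10 and 75 events: 61%, 56% and 48%. For 80% power at one-sided 0.05, the events needed are (1.645 + 0.842)² / (p(1 − p) × 2/9 × 0.762²), about 192 at p = 0.5 and 228 at p = 0.3. With 75 events the detectable ratio of HRs is about 3.4 (p = 0.5) to 3.8 (p = 0.3).

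**4. What a marker-only model reports.** Simulation: 105 patients, 70:35, uniform entry over 26.3 months, analysis at the 75th event, marker prevalence 50%, exponential PFS with median 4.9 months for marker-negative patients in both arms, two-sided 5% Wald tests, 400 runs (Monte Carlo SE at most √(0.25/400) = 2.5 points).

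| True marker HR | Marker-only: median HR | Marker-only: flagged | Interaction: flagged |
|---|---|---|---|
| 0.47 in both arms | 0.46 | 92% | 3% |
| 0.47 on MK-2206, 1 on everolimus | 0.60 | 58% | 33% |
| 0.68 on MK-2206, 2.14 on everolimus | 0.97 | 4.5% | 67% |
| 1 in both arms | 0.99 | 5% | 5% |

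Rows 1 and 2 both appear as protective markers. Nothing in the marker-only output says which kind of marker was found. A separate run with the design medians (4.9 and 8.2 months), censoring uniform from 2.7 to 29 months, 105 samples and 1,500 trials points the same way: for HR 0.5 on MK-2206 only, 49% (marker-only) against 32% (interaction); for HR 0.5 against 2.0, 16% against 82%.

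**The case against.** Four arguments on the other side carry weight.

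- **The interaction is already planned.** Section 13.4 evaluates it for CAF and karyotype on CR+PR+SD, the type of outcome named in the Section 1.2 CAF objective. The listed karyotype objective, impact on outcome, can be met by a prognostic Cox model. This stands and limits the gap to PFS and OS. It does not close it, because Appendix I defines its goal on PFS and OS.
- **Pooling is never stated.** The Appendix G sentence may name effects of interest and not a closed covariate list. The CAF-change model is expressly about one drug against the other, so arm is implied there. The earlier sorafenib work described in Appendix I looked for markers in each arm. This also stands: the fault is that the terms are not specified, not that the plan chose to ignore arm.
- **A reader might infer that these models can find only prognostic markers, or that a predictive marker is always averaged away.** The documents do not support that. A marker acting only on MK-2206 is flagged in about half of simulated trials, more often than by the interaction term. What is lost is the distinction. Near-complete loss needs opposite effects, an unfavourable case.
- **The interaction is poorly powered and would be tested many times.** The 27-plex and 23-plex panels alone give 50 markers; at one-sided 0.05, 50 × 0.05 = 2.5 chance findings are expected if none matters. Section 13.4 already calls this work exploratory and not open to powering. That is a reason to report estimates with intervals and an exploratory label. It is not a reason to let a main effect stand in for prediction.

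The missing strata are a separate, weaker matter of confounding and precision. Leaving them out does not make a model prognostic-only, and the documents give no figures from which to size the effect.

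**Conclusion.** The concern holds for the time-to-event models. As written, the Appendix G models and the multivariable CAF model cannot tell a marker that is prognostic under both drugs from one that predicts benefit from one drug, and they can miss a marker with opposite effects. The CAF-change model implies arm but leaves the terms unwritten. It would be too strong to say that the biomarker plan has no interaction or that the arms will knowingly be pooled.

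The simulated sizes rest on 50% prevalence and the marker effects shown. The power range of 29% to 46% rests on a ratio of HRs of 2.14 (borrowed from Appendix G's two-group HR), one-sided 0.05, 57 to 75 events and prevalence of 20% to 50%. Because tissue and blood are optional, event counts could be lower. Appendix G's figure above 90% should not be read as power for a predictive effect. These are exploratory objectives, so the point bears on how marker findings are reported and not on the trial's main conclusion.

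**What to change.** In Appendix G item 6 and in both Appendix I Cox models, specify PFS and OS on marker + arm + arm-by-marker, adjusted for MSKCC group and type of prior therapy. Keep arm in the model during AIC selection. Report the marker main effect as prognostic, stating how arm and marker are coded. Describe a marker as predictive only on the interaction HR with its CI, labelled exploratory, and state how many markers were examined. Add to Appendix G that its power statement refers to a two-group comparison, and give the interaction power beside it.

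The cost is appendix wording and a few degrees of freedom. Arm and both strata are already needed for randomization, so no new data are required. Section 13.3 does not list the categories of prior therapy; with 57 to 75 events the coding should be kept coarse. The real price is wide intervals: most interaction estimates will be inconclusive, and the report should say so.
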